- (k) Procedures only performed during the first 2 years of -subject participation in the study (eg, until last scheduled visit [Y3-YEV]) or EDV/FV in case the subject discontinues participation within the first 2 years).
- (l) The C-SSRS assessment will be implemented by site per IRB/IEC approval and upon completion of required training. As of the time of Protocol Amendment 6, all subjects had completed their Entry Visit. Thus, the C-SSRS was not assessed for any subjects at their Entry Visit.
- (m) For subjects that may transition to another BRV study or a managed access program or similar type of program, the EDV will need to be completed, however down-titration and FV may not be applicable.

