## 8.4 Study Duration

This study will run throughout the duration of the clinical development period of BRV, and will continue until a marketing authorization is granted by any Health Authority in an indication of the adjunctive treatment in adults with refractory POS, whether or not secondarily generalized, until the Sponsor decides to close the study, until subjects transition to another BRV study, until a managed access program, named patient program, compassionate use program, or similar type of access program is established as allowed per country-specific requirement in addition to legal and regulatory guidelines, or until BRV development is stopped by the Sponsor.

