#### **10.1.2 Dosing Schedule**

Subjects coming from BRV studies have the opportunity to access BRV treatment at a flexible dose of up to a maximum of 200 mg/day in b.i.d. administration. It is recommended that the daily dose be divided equally, taken with or without food, and that the first intake will be in the evening of the day of the dispensation of the study medication.

The individual starting dose of each subject will be the one defined/reached at the end of the previous study. It is recommended that the dosing be done in even increments such as 20 mg, 30 mg, 40 mg, etc. with the implementation of the IVRS/IWRS.

At each subject visit, if necessary, the dosage can be adapted:

- Up-titration can be made by increments of maximum 50 mg/day on a weekly basis and this to a maximum of 200 mg/day.
- Dose decreases can be made by steps of maximum 50 mg/day on a weekly basis. A last down-titration step at 20mg/day for 1 week will be included prior to the study-drug free period.

At each visit, an IVRS/IWRS will be responsible for issuing subjects kits of study medication, as appropriate, according to the visit schedule and according to the supplies needed by the subject in terms of number of containers of each size (80 or 200) and of each dosage (10 mg or 25 mg tablets) according to the dose prescribed and the possibility to down-

titrate/up-titrate by a maximum of 50 mg/day steps. Containers of 80 tablets will be progressively removed.

In case the subject will not continue with BRV, the Investigator will plan the progressive down-titration of the study drug. The down-titration period will be followed by a period free of study drug of minimum 2 weeks and a maximum of 4 weeks and subsequently the Final Visit will occur.

At the time of study termination by the Sponsor (as defined in Section 8.4), subjects will discontinue the study drug following the described down-titration process or will be converted without down-titration to commercial BRV, when and where available. Alternatively, subjects may transition into another BRV study, or be initiated without down-titration in a managed access program, named patient program, compassionate use program, or similar type of access program as allowed per country-specific legal and regulatory requirements.

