#### ***11.2.5 Early Discontinuation Visit***

- Vital signs including blood pressure and pulse rate.
- Body weight.
- Physical and neurological examination.
- ECG
- Retrieval of previous subject DRC.
- Recording of seizures.
- Laboratory assessment including safety (hematology, blood chemistry, and urinalysis), urine pregnancy test (if applicable).
- Recording of Adverse Events.
- Assessment of suicidality (C-SSRS).
- Medical procedures.
- Concomitant medications (AED and Non-AED) documentation.

- Drug return/accountability including study medication intake and compliance check.
- Dispensation of new DRC.
- Dispensation of study medication with down-titration dosing schedule.
- Appointment for the next visit according to the schedule described in Section 5.2.

Down-titration may not be applicable to subjects who may transition to another BRV study or may be initiated in a managed access program or similar type of program.

The following assessments will be performed only if the EDV occurs within the first 2 years.

- QOLIE-31-P questionnaire (except if subject mentally impaired and except for all subjects coming from N01193). The questionnaire should be filled in at the beginning of the Visit.
- HADS questionnaire (except if subject mentally impaired and except for all subjects coming from N01193). The questionnaire should be filled in at the beginning of the Visit, after the QOLIE-31-P.
- Healthcare provider consultation not foreseen by protocol
- Recording of workdays and schooldays lost and days subject received help from a caregiver (paid or not) at home.
- Hospital stay.
- EQ-5D questionnaire (except if subject mentally impaired and except for all subjects coming from N01193).
- Socio-professional data.

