| Month | Visit | Type of Visit | Month | Visit | Type of Visit |
| 1st year Follow-up | | | 1st year Follow-up | | |
| M0 | V1 | Entry Visit | M0 | V1 | Entry Visit |
| M1 | V2 | MEV | M1 | V2 | MEV |
| M2 | V3 | FEV | M2 | V3 | FEV |
| M3 | V4 | MEV | M3 | V4 | MEV |
| M4 | V5 | FEV | M4 | | |
| M5 | V6 | MEV | M5 | | |
| M6 | V7 | FEV | M6 | V5 | FEV |
| M7 | | | M7 | | |
| M8 | | | M8 | | |
| M9 | V8 | FEV | M9 | V6 | MEV |
| M10 | | | M10 | | |
| M11 | | | M11 | | |
| 2nd and subsequent years Follow-up | | | 2nd and subsequent years Follow-up | | |
| M12 | V9 | YEV | M12 | V7 | YEV |
| M15 | V10 | MEV1 | M15 | V8 | MEV1 |
| M18 | V11 | FEV | M18 | V9 | FEV |
| M21 | V12 | MEV2 | M21 | V10 | MEV2 |

FEV=Full Evaluation Visit; MEV=Minimal Evaluation Visit; M=month, V=Visit, YEV=Yearly Evaluation Visit

All subjects should have a Visit 1 at the start of N01199. Visit 1 will typically correspond to the last visit from the previous study and should be the visit at which study drug is dispensed for N01199. However, some subjects had a delay in treatment with study medication after completion of the previous study. Such subjects may have had an additional Supplemental Entry Visit (SEV) at the time of entry into N01199.

This study will run throughout the duration of the clinical development period of brivaracetam, and will continue until a marketing authorization is granted by any Health Authority in an indication for the adjunctive treatment in adults with refractory POS, whether or not secondarily generalized, until the Sponsor decides to close the study, until a managed access program, named patient program, compassionate use program, or similar type of access program is established as allowed per country-specific requirement in addition to legal and regulatory guidelines, or until brivaracetam development is stopped by the Sponsor.

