3.2.4 Study periods

The study is divided into 3 periods: Evaluation Period, Down-Titration Period, and Post-Treatment Period. A subject is classified as “discontinued” if the subject has a termination case report form (CRF) or has an early discontinuation visit (EDV). A subject is classified as “completed” if this subject completes the full extent of the study as defined in the protocol at database lock.

A “discontinued” subject can be potentially slotted into the 3 periods of the study. The following algorithms will be used to slot the subject appropriately into the Evaluation Period, Down-Titration Period, and Post-Treatment Period.

- For Evaluation Period, the start date is the date of first dose of BRV, and the following algorithm is used to determine the end date:
 - If the subject enters the Down-Titration Period, then the date of EDV is the end date;
 - If the subject does not enter the Down-Titration Period but meets 1 of the following criteria, the Evaluation Period ends on date of last dose of BRV:
 - Without an EDV but having a termination CRF,
 - With an EDV and having a termination CRF,
 - With an EDV and the date of EDV prior to the database lock date and having no termination CRF.
- A subject is considered entering Down-Titration Period only if the subject has an EDV and at least 1 dose of study drug after the date of EDV, the start date of Down-Titration Period is set as 1 day after the date of EDV, and the Down-Titration Period ends on date of last dose of BRV. A subject without an EDV but having a termination CRF or with an EDV but without any dosing of study drug after the EDV will not have the Down-Titration Period, and no artificial Down-Titration Period will be created for analysis.
- A subject is considered entering the Post-Treatment Period if the subject has at least 1 contact (scheduled visit, unscheduled visit, or telephone contact) after the date of last dose of BRV. The Post-Treatment Period starts 1 day after date of last dose of BRV irrespective of entering the Down-Titration Period, and there is no end date.

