A “completed” subject can potentially have Evaluation Period, Down-Titration Period, or Post-Treatment Period. At the time of study termination by the Sponsor, subjects will discontinue the study drug following the down titration process or will be converted without titration to commercial BRV where available; alternatively, subjects may be initiated without down-titration in a managed access program, named patient program, compassionate use program, or similar type of access program as allowed per country specific requirements in addition to legal and regulatory guidelines.

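### In SAP 3.2.4 an early discontinuation visit alone makes a subject discontinued, so a subject who moves to an access programme or another BRV study at sponsor closure also meets the completed definition, and no precedence is stated

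*SAP*

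**What the plan says.** SAP 3.2.4 gives two end-of-study classes. A subject is discontinued "if the subject has a termination case report form (CRF) or has an early discontinuation visit (EDV"), so either record is enough. A subject is completed "if this subject completes the full extent of the study as defined in the protocol at database lock". The paragraph on completed subjects then describes exits at sponsor termination, including this one: "alternatively, subjects may be initiated without down-titration in a managed access program".

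The protocol asks for an EDV on the transition routes. Table 5:1, footnote (m), covers subjects who may move to another BRV study or an access programme: "the EDV will need to be completed, however down-titration and FV may not be applicable". Section 11.2.5, which describes the EDV, names the same subjects: "Down-titration may not be applicable to subjects who may transition to another BRV study or may be initiated in a managed access program". For sponsor closure, Protocol 10.1.2 says "Alternatively, subjects may transition into another BRV study, or be initiated without down-titration in a managed access program", and 11.1.26 repeats both routes. Section 11.1.26 treats a subject as having completed if he or she took part up to the point at which the study was halted.

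SAP 5.1 reports completed and discontinued counts. Its Kaplan-Meier analysis of time on treatment counts permanent discontinuation as an event at last dose and censors completers at last dose.

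**The concern.** The EDV rule is an operational rule that a programmer can apply as written. For a subject who stays until closure and then moves to an access programme or another BRV study, it returns *discontinued*, while the protocol's definition of completion returns *completed*. The SAP expects records with an EDV and no termination CRF, because its period rules include that case. For a discontinued subject without a termination CRF, SAP 5.1 gives the reason as missing.

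Two outputs are at stake: the completed/discontinued split and, if it uses the same class, the Kaplan-Meier retention estimate. These subjects continue on BRV, so counting them as events would understate retention in a study of long-term tolerability.

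**Working it through.** The plan gives no figure to reproduce: SAP 2.4 reports no sample size calculation and SAP 3.1 plans no hypothesis test. The check is mainly textual.

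**1. Both definitions applied to each kind of exit**

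| Exit | EDV called for? | Discontinued by the EDV rule? | Completed? |
|---|---|---|---|
| At closure, Final Visit (FV) at sponsor request (Protocol 11.2.7) | Not stated | No, if no EDV | Yes |
| At closure, to commercial BRV | Not named in footnote (m) | Not shown | Yes |
| At closure, to an access programme | Yes, footnote (m) | Yes | Yes (Protocol 11.1.26, SAP 3.2.4) |
| At closure, to another BRV study | Yes, footnote (m) | Yes | Yes (Protocol 11.1.26) |
| Before closure, to either | Yes, footnote (m) | Yes | Not under Protocol 11.1.26 |

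Rows three and four meet both definitions.

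**2. Is there a tie-break?** Table 5:1, footnote (j), calls subjects with an EDV discontinued and subjects leaving at the end of the programme completed, which repeats the overlap. SAP 5.1 covers subjects with more than one discontinuation reason but gives no precedence between the two classes.

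**3. Effect on the disposition split.** N = 668 enrolled (SAP 2.4). One subject moves the split by 1/668 = 0.150 points. The documents give no count k of affected subjects. For assumed k = 10, 33 and 67:
- 10/668 = 1.50 points
- 33/668 = 4.94 points
- 67/668 = 10.03 points

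**4. Effect on the Kaplan-Meier estimate.** Recoding one exit at time u from censored to event multiplies the estimate at every t at or after u by 1 − 1/n(u), where n(u) is the number at risk at u. The fall at landmark t is S(t)/n(u), where S(t) is the estimate with that exit censored. For t before u it is zero.
- Assume 334 earlier discontinuations, no earlier censoring and no further events up to t. Then n(u) = 668 − 334 = 334, S = 0.50, and the fall is 0.50/334 = 0.150 points (50.00% to 49.85%).
- Assume also that 100 subjects were censored before u and S is still 0.50. Then n(u) = 234 and the fall is 0.50/234 = 0.214 points (50.00% to 49.79%).
- Further events between u and t lower S(t) and so reduce the fall.

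**5. Which exits count.** The last listed landmark is 60 months, and SAP 3.2.5 uses 30-day months, so it lies at 60 × 30 = 1800 days. Exits after day 1800 change no listed estimate. SAP 3.2.7 defines exposure as last dose minus first dose plus 1. Suppose closure, with last dose at closure, is no earlier than 15 Oct 2015, the date of the current protocol. From 11 Nov 2010 to 15 Oct 2015 is 1799 days, giving 1800 days of exposure. Only subjects first dosed on or after 11 Nov 2010 could then change a listed estimate, and a later closure moves that date later. The documents give no entry dates.

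**6. Scale under assumed inputs.** A simulation took 668 subjects, closure uniformly 36 to 108 months after entry, 15% discontinuation a year, and 200 runs per scenario. The 60-month estimate was about 44% with closure-time transitions censored. With them counted as events it was about 40%, 36% or 29% when 25%, 50% or 100% of remaining subjects transitioned with an EDV. Over 10% to 25% discontinuation a year the fall ranged from about 2 to 20 points. The 36-month estimate did not move because no closure was assumed before then. None of these inputs comes from the documents.

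**The case against.** **The SAP already signals the intended reading.** It puts access-programme entry at closure under completed subjects. It also says a completed subject can have a Down-Titration Period, which its period rules allow only after an EDV. This has weight, but those period rules are introduced for discontinued subjects and the SAP does not say that they apply to completers. The intention can be guessed, but the stated rule still gives the opposite answer.

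**Footnote (m) may concern only transfers before closure.** Neither it nor Protocol 11.2.5 mentions closure, and if they exclude it the overlap disappears. Application at closure is an inference. It is well supported, because the footnote has no timing limit and Protocol 10.1.2 and 11.1.26 list the same routes at closure.

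**The pre-analysis data review (Protocol 13.4) could settle individual cases.** It could, but it has no stated rule to apply to them.

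**The study is descriptive.** This stands and limits the severity.

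**The SAP's omission of the other-BRV-study route is editorial.** This also stands. SAP 2.3 reads "until the Sponsor decides to close the study, until a managed access program, named patient program, compassionate use program", where Protocol 8.4 has "until subjects transition to another BRV study, until a managed access program". The SAP's completed definition defers to the protocol, so the route is covered.

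A reader might also infer that everyone remaining at closure is misclassified. Protocol 11.2.7 provides a sponsor-requested FV that need not follow an EDV, and footnote (m) does not name commercial conversion, so the documents do not support that. Nor do they show that the termination-CRF limb captures completers, because the SAP does not define that form.

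**Conclusion.** The conflict is real and should be fixed. Subjects ongoing at sponsor closure who have an EDV for transition to an access programme or another BRV study meet both definitions, and the EDV rule taken literally reports them as discontinued. This rests on footnote (m) applying at closure. The Kaplan-Meier consequence also requires that analysis to use the SAP 3.2.4 class.

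The size is unknown. Each affected subject shifts the disposition split by 0.15 points. The effect on the listed Kaplan-Meier estimates depends on how many such exits occur by each landmark, and may be zero. A reader might take the simulated fall of 2 to 20 points as the bias in this trial. The documents do not support that, since they give no entry dates, closure date or transition count.

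Ordinary completers without an EDV, the primary safety variables and the adverse-event disposition row are not shown to be affected. Classing transfers before closure as discontinued is defensible and is the sponsor's choice.

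**What to change.** In SAP 3.2.4, state that a subject ongoing at sponsor closure whose EDV was done only for transition to another BRV study or an access programme is completed, regardless of the EDV.

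Determine this from the closure date, the dosing and visit records, and the reason that Protocol 9.3 requires on the CRF. Do not rely on the end-of-study status: Table 5:1, footnote (j), has it completed at the FV, and footnote (m) says the FV may not apply to these subjects. For the same reason, do not fall back to the EDV rule when that status is missing, as this would recreate the error.

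In SAP 5.1, state that these subjects are censored at last dose in the Kaplan-Meier analysis, and state how transfers before closure are classed.

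The cost is a few sentences of SAP text, minor derivation work on data already collected, and manual review of transition records without an FV.

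Optional additions are a separate disposition row for transitions, and the other-BRV-study route in SAP 2.3 and 3.2.4 for consistency with the protocol.

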#### **11.2.7 Final Visit (FV following a Study Drug Free Period after an EDV or FV initiated upon Sponsor request at the end of the program)**

- Vital signs including blood pressure and pulse.
- Body weight and height (only for those subjects still potentially growing).
- Physical and neurological examination.
- ECG (except after an EDV when EDV ECG results were normal).
- Retrieval of previous subject DRC.
- Recording of seizures.
- Recording of workdays and school days lost and days subject received help from a caregiver (paid or not) at home during the first 2 years.
- Hospital stay during the first 2 years.

- Healthcare provider consultation not foreseen by protocol during the first 2 years.
- Laboratory assessment including safety (hematology, blood chemistry, and urinalysis), urine pregnancy test (if applicable).
- Recording of Adverse Events.
- Assessment of suicidality (C-SSRS).
- Medical procedures.
- Concomitant medications (AED and Non-AED) documentation.
- Drug return/accountability including study medication intake and compliance check.
- Completion of end of study status.
- Retrieval of “Clinical Study Subject Card”.

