Titration Period during which the dose of BRV is decreased in steps of 50mg/day on a weekly basis with a last down titration step at 20mg/day for 1 week. Subjects who have completed the Down-Titration Period or subjects who discontinue during the Evaluation Period without entering the Down-Titration Period enter a Post-Treatment Period for a minimum of 2 weeks and a maximum of 4 weeks and subsequently, the final visit will occur.

The maximum allowable daily dose for this study was increased from 150mg/day to 200mg/day based on amendment 6 to the protocol. It is recommended that the daily dose be administered in 2 equal intakes.

Dose adjustment to concomitant AEDs may be made at any time during the study and subjects may start new AEDs. Concomitant AEDs may also be discontinued; however, special considerations apply if the discontinuation of such AEDs results in the subject receiving BRV monotherapy. Previously, in the event of excellent efficacy and tolerability of BRV, withdrawal of concomitant AEDs resulting in monotherapy of BRV may have been attempted by the Investigator. With protocol amendment 6, conversion to monotherapy was no longer permitted; however, subjects already on BRV monotherapy are allowed to continue monotherapy treatment.

The visit schedule for this study depends on the previous study from which the subject was enrolled and the numbering of study visits differs depending on the previous study. Study visits at Months 6, 12, 18, 24, and so forth are either Full Evaluation Visits (FEVs) or Yearly Evaluation Visits (YEVs) at which a greater number of assessments are performed for all subjects from previous studies. For subjects coming from N01193, study visits at Months 1, 3, 5, 15, and 21 are minimal Evaluation Visits (MEVs) at which few assessments are generally performed. Study visits at Months 2, 4, and 9 are FEVs. For subjects coming from N01252, N01253, and N01254, study visits at Months 1, 3, 9, 15, 21 are MEVs. The study visit at Month 2 is an FEV. In addition, a phone call is scheduled at the end of the Down-Titration period and a Drug-Free Final Visit (FV) is scheduled at the end of the Post-Treatment Period. The study schedule just described is shown in [Table 2-1](#).

Table 2–1: Study Schedule

| Subjects coming from Exploratory Study (N01193) | | | Subjects coming from Confirmatory Studies (N01252, N01253, N01254) | | |
|--|-------|---------------|--|-------|---------------|

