2.4 Determination of Sample Size

No sample size calculation was done. Sample size was dependent upon recruitment into and completion of preceding studies. At the time of development of this SAP, the study enrollment has been completed; a total of 668 subjects were enrolled into N01199.

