3 DATA ANALYSIS CONSIDERATIONS

3.1 General presentation of summaries and analyses

Statistical analysis and generation of tables, figures, subject data listings, and statistical output will be carried out using SAS® Version 9.1 or higher.

Descriptive statistics, such as the mean, standard deviation (SD), median, 25th percentile, 75th percentile, minimum value, and maximum value for quantitative variables, and counts and percentages for categorical variables, will be provided. Denominators for percentages will generally be based on the set of subjects with at least 1 assessment at the time point or at least 1 assessment during the time interval being summarized.

All summaries will be descriptive; no statistical hypothesis testing is planned.

Unless otherwise noted, summaries will present BRV overall, which will include all subjects exposed to BRV during the study.

Subject data listings will be provided and will present source data and key derived variables for statistical analyses.

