11.2.2 General summaries of TEAEs

Pre-treatment AEs will be provided in a subject data listing; no summaries of pre-treatment AEs are planned.

An overall summary of AEs will provide the overall number of TEAEs and the numbers and percentages of subjects with at least 1 TEAE, with a TEAE that led to permanent discontinuation of study drug, with a drug-related TEAE, with a severe TEAE, with a treatment-emergent SAE, and with a drug-related treatment-emergent SAE. The number and percentage of subjects who died will also be summarized. This summary will be provided for all subjects in the Safety Analysis Set and also by subgroup for geographic region and seizure type.

The following summaries of TEAEs will be provided by MedDRA SOC and PT. All summaries are for the combined Evaluation, Down-Titration, and Post-Treatment Periods unless otherwise indicated.

Overall Incidence Summaries

- Incidence of TEAEs
- Incidence of TEAEs by 3-month time interval
- Incidence of TEAEs by study period (Evaluation, Down-Titration, Post-Treatment)
- Incidence of TEAEs for TEAEs occurring in at least 5% of subjects
- Incidence of TEAEs by 3-month time intervals for TEAEs occurring in at least 5% of subjects overall
- Incidence of non-serious TEAEs occurring in at least 5% of subjects

The incidence of TEAEs occurring in at least 5% of subjects will be summarized overall as noted above and also by subgroup for geographic region, seizure type, and randomized treatment from the previous double-blind study.

A subject is included in a 3-month interval if the subject was receiving BRV at any time during that interval based on their duration of exposure to BRV (eg, a subject with exposure for 91 days is included in the time interval for Months 1-3 and Months 4-6). Summaries of AEs by 3-month intervals will include all subjects who are classified into each time interval

as defined above. TEAEs which had onset prior to or on the date of the last dose of BRV are included in summaries by 3-month time intervals.

Maximum Intensity and Causality

- Incidence of TEAEs by maximum intensity
- Incidence of drug-related TEAEs

Serious Adverse Events

- Incidence of treatment-emergent SAEs

Discontinuations due to TEAE

- Incidence of TEAEs leading to permanent discontinuation of study drug

TEAEs of interest

AEs of interest will be identified based on MedDRA search criteria, which are documented outside of the SAP. The following summaries will be provided for AEs of interest:

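### Post-Treatment TEAEs and Final Visit safety rows can mix subjects still taking BRV with drug-free subjects, because SAP 3.2.4 never asks whether BRV has stopped

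*SAP*

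**What the plan says.** SAP 3.2.1 takes the last dose of BRV to be the last one within the study's own periods. BRV from another supply does not move that date.

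SAP 3.2.4 calls a subject discontinued if there is an EDV or a termination CRF. For these subjects, one contact after the last dose, even by telephone, opens the Post-Treatment Period: "The Post-Treatment Period starts 1 day after date of last dose of BRV irrespective of entering the Down-Titration Period". No end date is set. For completed subjects the section says only that they may have any of the three periods, and gives no dating rule. In the same paragraph it foresees that at sponsor termination some subjects "will be converted without titration to commercial BRV where available", or start an access programme without a taper. Protocol 10.1.2 and 11.1.26 list the same routes and add transfer to another BRV study.

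On the last visit, SAP 2.3 states that "a Drug-Free Final Visit (FV) is scheduled at the end of the Post-Treatment Period". The title of Protocol 11.2.7 covers two kinds of FV: one after a study-drug-free period, and an "FV initiated upon Sponsor request at the end of the program". For subjects moving to another BRV study or an access programme, footnote (m) to Protocol Table 5:1 says "the EDV will need to be completed, however down-titration and FV may not be applicable".

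Two sets of outputs depend on these definitions. SAP 11.2.2 plans "Incidence of TEAEs by study period (Evaluation, Down-Titration, Post-Treatment"). SAP 11.3.1, 11.3.2, 11.4.1 and 11.4.2 summarise laboratory values, vital signs, weight and ECG at a single FV time point.

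**The concern.** A column headed Post-Treatment, or a row for a visit that the design summary calls drug-free, will be read as describing subjects off BRV. A subject who changes supply without a break has left study medication but not the drug. If that subject has a later contact, an event arising on continued BRV is tabulated as post-treatment. If that subject has an FV, its laboratory, vital-sign, weight and ECG values share a row with values taken two to four weeks after stopping.

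This is a foreseen way out of the study. Protocol 8.4 keeps the study open until, among other things, BRV is authorised or an access programme exists. What is at stake is how the planned tables for the time after study drug are read, in a study whose primary objective is long-term safety and tolerability.

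**Working it through.** There is no planned figure to reproduce: "No sample size calculation was done", and the analysis is descriptive. The check traces subjects through the rules and then sorts the outputs.

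**Three routes out**

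1. *Taper, drug-free interval, FV.* Study dosing ends, two to four weeks without study drug follow, and the FV takes place. The Post-Treatment Period and the FV mean what their labels suggest.
2. *Transfer to an access programme or another BRV study, with an EDV.* The EDV makes the subject discontinued under SAP 3.2.4, so the dating rule applies. A visit or call after the last study dose opens a Post-Treatment Period while the subject is taking BRV. With no later contact there is no such period. If the FV is waived under footnote (m), the subject is absent from the FV rows.
3. *Conversion to commercial BRV at programme end.* Footnote (j) to Table 5:1 has completers' end-of-study status recorded at the FV. SAP 3.2.4 gives them no dating rule. If the rule for discontinued subjects were carried over, an FV after the last study dose would put the subject in both the Post-Treatment Period and the FV rows. An FV on the day of the last study dose would put the subject in the FV rows only, because those are built by visit.

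Later contacts are plausible on routes 2 and 3. Protocol 12.2.2 requires SAEs known to the investigator to be reported for up to 30 days after study medication is withdrawn. SAP 11.2.1 sets no upper time limit on a TEAE.

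**Outputs affected**

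- TEAEs by study period: the Post-Treatment column.
- FV rows for laboratory parameters (including PCST by visit), vital signs, weight and ECG.

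**Outputs not affected**

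- TEAE incidence over the combined periods (SAP 11.2.2).
- TEAEs by 3-month interval, which count onsets up to the last dose (SAP 11.2.2).
- Last Value (SAP 3.2.6), on-treatment PCST (SAP 11.3.1, 11.3.2, 11.4.1) and the overall on-treatment ECG summary (SAP 11.4.2), all bounded by the last dose.

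**Size**

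Let c be the share of subjects in an affected summary who are still on BRV, and r_on and r_off the rates on and off drug.

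- Pooled rate = c × r_on + (1 − c) × r_off
- Pooled rate − r_off = c × (r_on − r_off)

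For an assumed difference of 10 percentage points:

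- c = 10%: 0.10 × 10 = 1 point
- c = 30%: 0.30 × 10 = 3 points
- c = 50%: 0.50 × 10 = 5 points

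Both c and the 10 points are assumptions. SAP 2.4 gives 668 enrolled but not how many left by each route. The identity also assumes that converters otherwise resemble the remaining subjects.

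One feature could raise c in particular rows. Footnotes (e) and (i) to Table 5:1 waive the FV ECG and laboratory tests after an EDV with normal results. Some drug-free FVs then contribute no such data, while a sponsor-requested FV without an EDV still does.

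**The case against.** The strongest reply is that nothing in the plan compares on-drug with off-drug time. The SAP says "All summaries will be descriptive; no statistical hypothesis testing is planned", and the primary variables are summarised over the combined periods. This stands. A reader might infer that the study's only internal contrast is compromised. The documents do not support that: no such contrast is planned, and change from the prior study's Baseline is also summarised.

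Second, the drug-free label for the FV appears only in the design summary in SAP 2.3. The analysis sections say FV and make no claim about recovery, and Post-Treatment can be read as relative to study treatment. This also stands, but a table reader has no means of telling which subjects were off BRV.

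Third, footnote (m) removes some FVs, and a subject without later contact has no Post-Treatment Period. This reduces the mixing without excluding it. The footnote is permissive, does not name commercial BRV, and does not stop a phone contact from opening the period.

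Fourth, a clean off-drug group would not follow from removing converters. Because of the waivers, FV laboratory and ECG data after an EDV are weighted towards abnormal EDV results. Separation gives correctly labelled groups, not a recovery estimate.

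A reader might also infer that full-dose study drug taken after an EDV, while waiting for the new supply, would be labelled Down-Titration, since SAP 3.2.4 asks only for an EDV and a later dose. No passage describes such bridging, and Protocol 11.2.5 dispenses EDV medication with a down-titration schedule. No change to the Down-Titration rule is warranted on this evidence.

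**Conclusion.** The concern holds within limits. SAP 3.2.4 dates the Post-Treatment Period from the last study dose without checking that BRV has stopped, leaves it open-ended, and gives completers no rule, although both documents foresee uninterrupted BRV from another source. No flag, exclusion or split by continued use was found.

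The consequence is confined to the Post-Treatment column of TEAEs by study period and the FV laboratory, vital-sign, weight and ECG rows. The overall safety conclusions do not depend on it. The size is unknown: the 1 to 5 points shown above rest on assumed inputs and are not an estimate for this trial. The conclusion assumes only that some subjects take a foreseen conversion route and have an FV or another contact after the last study dose.

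**What to change.** In SAP 3.2.4, add one rule for discontinued and completed subjects alike that classifies status after the last study dose as:

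- drug-free;
- continued non-study BRV (commercial supply, access programme or another BRV study);
- unknown.

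Derive it from the recorded end-of-study status, the specified other reason for discontinuation, EDV data and medication records. Present Post-Treatment TEAEs and all FV summaries for drug-free subjects separately from the other two groups. Leave overall TEAE incidence as it is.

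The unknown group is needed because the data may be thin. The discontinuation reasons in SAP 5.1 have no transfer category. Protocol 10.2 asks for records of treatments other than BRV, while Protocol 11.1.18 asks for all medications, so capture of non-study BRV cannot be taken for granted.

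The cost is SAP wording, one derived variable that may need record review, and extra columns in a few tables. Denominators for the drug-free summaries shrink, and some subjects will stay unclassified. No new data collection or change in subject management is involved.
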